1 PROTOCOL SUMMARY

Title:	Evaluation of cigarette package inserts for enhanced communication with smokers
Grant Number:	R01 CA215466
Study Description:	A randomized controlled trial was conducted to assess the influence of cigarette package inserts with messages about the benefits of cessation and tips for quitting on smoking cessation- related psychosocial and behavioral outcomes. We hypothesized that inserts would promote these outcomes and that these effects would be enhanced when cigarette packages included both inserts and pictorial warning labels. In this 2X2 between-subject trial (i.e., inserts with efficacy messages vs. no inserts; pictorial warnings vs. text-only warnings), participants received a 2-week supply of their preferred cigarette brand variety, with labeling to reflect their experimental condition.
Objectives:	To evaluate the impact of inserts on smoking cessation-related outcomes using a randomized controlled trial among adult smokers.
Endpoints:	Data were collected over 14 days using a study smartphone. Participants were instructed to log every cigarette they smoked during this period. Approximately 4-5 times a day, participants were prompted to complete a brief, 1-3 minute survey immediately after they indicated that they had smoked, with cigarette logs sampled using an algorithm based on self- reported baseline smoking frequency. Each evening, between 7 and midnight, participants were instructed to respond to an evening survey using the smartphone app, which took 1-3 minutes to complete.
	Primary Endpoints : Self-efficacy to Quit Smoking; Self-efficacy to Cut Down on Smoking; Worry About Harms from Smoking; Strength of Feeling About Smoking; Extent of Motivation to Quit; Talk About Smoking Cessation or Harms; Foregoing or stubbing out a Cigarette
	Secondary Endpoints : Strength of Hopefulness About Quitting; Satisfaction From Smoking; Cognitive Elaboration of Smoking Benefits; Cognitive Elaboration of Smoking Harms; Cognitive Elaboration of Cessation Benefits; Response Efficacy; Perceived Susceptibility to Smoking Harms; Cigarettes Per Day

Study Population:	Adult smokers in South Carolina and New York were recruited, with efforts to recruit people from lower socioeconomic status groups. Of 1818 people screened, 602 were ineligible, 773 either declined to participate or were unable to be scheduled for orientation, and 443 were eligible and randomized. Of these, 56 did not attend the study orientation, and 20 did not complete minimum criteria to be included in the analytic sample. The final analytic sample involved 367 people.
Description of Study Intervention/Experimental Manipulation:	The 2X2 between subject intervention involved randomization to one of four groups: a) control; b) inserts only; c) pictorial warnings only; d) inserts and pictorial warnings. Insert conditions included four rotating messages, two about cessation benefits and two with cessation tips. Warning text for all conditions included four rotating messages, with the text-only "control" condition used the current warning size and placement (i.e., 50% of one pack side), whereas pictorial warnings covered approximately 50% of the lower half of both the front and back of packs.
Study Duration:	June 28, 2019 to June 29, 2021
Participant Duration:	Study participation involved a 45-minute study orientation where potential participants completed a baseline survey, received training in the 14-day study, and were provided the study materials (i.e., smartphone, cigarette packs). After the 14-day observation period, participants completed a final survey and interview and received compensation.

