6 PARTICIPANT DISCONTINUATION/WITHDRAWAL

Participants could discontinue participation at any time. Clinically relevant findings were reported as an adverse event (AE). We discontinued participation for the following reasons:

- Significant study intervention non-compliance, as indicated by not logging any cigarettes or evening reports;
- Unable to contact study participant during any scheduled followup calls;
- Any event or medical condition or situation occurred such that continued collection of follow-up study data were not in the best interest of the participant or might have required an additional treatment that would confound the interpretation of the study.

The reason for participant discontinuation or withdrawal from the study were recorded. Those who signed the informed consent form and were randomized but did not receive the study intervention were replaced. Participants were also replaced if they signed the informed consent form, were randomized, received the study intervention, and subsequently withdraw, or if they were discontinued from the study.

A participant was considered lost to follow-up if study personnel were unable to contact the participant after at least 3 attempts. If the participant continued to be unreachable, he or she was considered to have withdrawn from the study with a primary reason of lost to followup.

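### Twenty randomised participants are excluded after orientation on undefined minimum criteria, so the 367 analysed are not the set as randomised

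*Protocol*

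**What the plan says.** The Protocol summary (section 1, Study Population) gives the flow. It counts 443 people as randomised and reports 56 of them lost because they missed the orientation session. About a second group it says that "20 did not complete minimum criteria to be included in the analytic sample". That leaves 367 analysed. It does not say what the minimum criteria were.

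Protocol section 6 lists the reasons for which the study ended participation. The first is "Significant study intervention non-compliance, as indicated by not logging any cigarettes or evening reports". The second is "Unable to contact study participant during any scheduled followup calls". The third covers events or conditions that made further data collection inadvisable or confounding. On replacement it states: "Participants were also replaced if they signed the informed consent form, were randomized, received the study intervention, and subsequently withdraw". The same sentence extends this to people whom the study discontinued.

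The SAP (Study design overview) planned to enrol 380 and expected 85% to finish with adequate data, giving 80 per cell. Adequate data is not defined either. The SAP names no as-randomised analysis set, reports no exclusions by arm, and plans no analysis that brings the excluded people back. Its Missing Data section confines multiple imputation to evening-report outcomes. The reason given is that, for cigarette surveys, a missing record could mean either that the person did not smoke or that they did not report.

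**The concern.** Randomisation makes the four groups comparable at assignment. An exclusion that depends on what people do after they have the packs can undo this, because the labels may influence that behaviour. The trial's own theory allows it: Protocol sections 2.1 and 2.2 describe avoidance and reactance, and H1 predicts foregone cigarettes and lower consumption. Logging is also close to the outcome, since SAP Table 3 defines cigarettes per day as the number of cigarette logs.

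Replacing people who leave restores the sample size. It does not restore comparability, because the replacements are not the people who left.

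The exclusion is also not needed for most outcomes. The mixed models in the SAP's Statistical design section accept partial records, so a participant with a few observations can contribute them under the assigned arm. If the 20 fell unevenly across arms and differed from the rest, every contrast based on the 367 would carry some bias. A reader cannot judge this from what is reported.

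**Working it through.** **1. Participant flow (Protocol section 1).**
- Randomised: 1818 − 602 − 773 = 443, as stated.
- Analysed: 443 − 56 − 20 = 367, as stated.
- Not counted as orientation no-shows: 443 − 56 = 387.
- All losses: 76/443 = 17.2%. No-shows: 56/443 = 12.6%. The 20: 20/443 = 4.5% of those randomised and 20/387 = 5.2% of the 387.

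The flow closes exactly, so there is no third excluded group. Anyone discontinued under section 6 is among the 56, the 20 or the 367.

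**2. Planned numbers (SAP, Study design overview).** 380 × 0.85 = 323, close to 4 × 80 = 320. Randomised exceeds the enrolment target by 443 − 380 = 63, which is compatible with replacement.

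**3. Possible bias in a main-effect contrast (H1 or H2).** The split of the 20 is not given, so these are assumed scenarios. Take 387/2 = 193.5 people per factor level. Let a and b be the numbers excluded at the two levels, with a + b = 20, and let k be the difference in SD between excluded and retained people. The full-set mean at a level is the retained mean plus (fraction excluded) × k, so with the same k at both levels:

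size of bias = (a − b)/193.5 × k

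| Split a/b | k = 0.5 | k = 1.0 |
|---|---|---|
| 10/10 | 0 | 0 |
| 15/5 | 0.026 | 0.052 |
| 20/0 | 0.052 | 0.103 |

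If excluded people differ in opposite directions at the two levels, the size is (a + b)/193.5 × k = 20/193.5 × k, or 0.052 to 0.103 SD for any split.

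**4. Binary outcome, worst case.** Setting every excluded person to 0 or 1 gives an interval for the difference of total width 20/193.5 = 0.103, about 10 percentage points. With a 10/10 split and similar retained rates this is ±10/193.5 = ±0.052, about ±5 points.

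**5. Scale.** SAP Table 6 gives detectable effects for H1 and H2 of 0.15 to 0.17 (daily data) and 0.07 to 0.08 (event data). The upper scenarios reach the event-data figure. That comparison makes the bias look relatively large, because Table 6 assumes a correlation of 0.40 and the SAP reports a mean ICC of 0.73 in the trial's own data. True detectable effects are larger than Table 6 states.

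**The case against.** Much of the case on the other side stands, and it limits the point.

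- **Cause.** A reader might infer that the 20 were removed for not logging. The documents say only minimum criteria. Section 6 also lists loss of contact and medical or other events. The link to logging is likely but unstated.
- **Lost responders.** A reader might infer that people who stopped smoking were dropped. The section 6 rule can mean that both cigarette logs and evening reports were absent, or that either was. Someone who stopped smoking but filed evening reports is caught only on the second reading. Entry required at least 10 cigarettes a day, so on the first reading a lost responder would have logged nothing and filed nothing.
- **Exposure.** It is tempting to treat all 387 as having received packs. Protocol section 4.1 does not support this. After COVID onset, Cornell participants completed orientation before collecting materials, while UofSC participants received materials before the Zoom orientation. Some attenders may have had no packs, and some no-shows may have had them.
- **Discarded data.** Section 6 says that people were replaced. It does not say that their data were thrown away.
- **Usable records.** The documents do not say what data the 20 provided. A person with no EMA record adds nothing to a mixed model.
- **Cigarettes per day.** This is a single log count per person, so the partial-records argument does not apply. Restoring sparse loggers would count non-reporting as low smoking.
- **Size.** The 17.2% is mostly the 56 no-shows, whose loss is hard to attribute to labels that most of them had not received.

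The SAP also foresaw 15% without adequate data and plans checks of missingness. Neither step restores the 20 or shows their arms.

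**Conclusion.** The point holds in a limited form. Twenty people, 5.2% of the 387 not counted as no-shows, leave the analysis after randomisation under a rule that neither document defines, with no breakdown by arm and no analysis that restores them. Section 6 makes it probable that at least part of this reflects behaviour after exposure.

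The likely bias is modest. It is nil if the 20 are balanced and alike, 0.03 to 0.05 SD for a 15/5 split and 0.05 to 0.10 SD if all 20 come from one level. These figures assume equal factor levels and a same-direction difference of 0.5 to 1.0 SD; the documents supply neither.

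The documents do not support a claim that responders were in fact lost, that the arms were unbalanced, or that binary contrasts could typically be wrong by 10 points in either direction. About 10 points is the full width of the worst-case interval.

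**What to change.** - **Repeated evening and cigarette-survey outcomes:** analyse as assigned every randomised participant who received packs and has at least one EMA observation. This applies whether or not they met the minimum criteria or were discontinued or replaced. Keep the 367 as a sensitivity analysis.
- **Exposed participants without evening reports:** include them through the multiple imputation already planned for evening outcomes, or show bounds.
- **Cigarettes per day:** do not read absent logs as zero smoking. Keep the 367 and add bounds for those excluded, because the SAP states that not smoking and not reporting cannot be separated.
- **Reporting:** state the minimum criteria. Tabulate the 56 and the 20 by arm, with reasons and whether packs were received.

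The cost is SAP wording and a re-run on existing records, with slightly noisier data from poor compliers. No new data collection is needed.

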2 INTRODUCTION

2.1 STUDY RATIONALE

Smoking is the leading cause of preventable disease in the US, killing 480,000 people a year.¹ Cigarette package labeling is a fundamental tobacco control policy^{2 3} that specifies how health messages are communicated to the 40 million people who smoke in the US.^{4 5} Smokers are exposed to their packs thousands of times a year, which makes packaging the most reliable, cost-effective vehicle for governments and industry to communicate with smokers. Reflecting this principle, the World Health Organization's Framework Convention on Tobacco Control (FCTC) recommends large, pictorial health warning labels (HWLs) printed on the exterior of cigarette packs to communicate about smoking-related risks.⁶ More than 100 countries have adopted pictorial HWLs,⁷ but only Canada uses inserts to enhance HWL effectiveness.

"Inserts" and "onserts" (hereafter "inserts") are small, printed leaflets that are removable material found inside or attached to the outside of product packaging (Figure 1). Tobacco companies have long used inserts to reach smokers with promotional materials and messaging (e.g., coupons, contests, product information).⁸⁻¹⁰ Smokers are exposed to inserts every time they open a new pack, which is much more often than inserts for pharmaceutical drugs that are purchased much less frequently than cigarettes. Because of their high exposure frequency, cigarette inserts need not include all pertinent

information, allowing for rotating messages that address key limitations of drug inserts (e.g., concise, legible, use of imagery).¹¹⁻¹³ For example, Canada currently includes 8 different inserts that rotate across packs. One-third of Canadian smokers report reading inserts in the prior month,¹⁴ which would be equal to 12 million US smokers engaging with insert content each month. The US Food and Drug Administration (FDA) has regulatory authority to use inserts for communication with consumers¹⁵ and is developing pictorial HWL content for implementation in 4-5 years.^{16 17} The FDA can change its labeling policy to reflect scientific understanding, whether for upcoming or subsequent labels.¹⁸

Studies of cigarette labeling have focused almost exclusively on HWLs about the negative consequences of smoking, generally finding that large pictorial HWLs promote smoking cessation.^{5 19 20} These studies have identified the central role of negative affect in mediating HWL effects on cessation-related intentions and behaviors.²¹⁻²⁶ However, some research and theory cautions that "fear appeals" – like HWLs that graphically portray negative health consequences from smoking – may be ineffective when people are scared but do not see an effective way to avoid the danger that the message highlights.²⁷⁻³⁶ Rather than quit smoking, smokers could deny the relevance of the message (denial), not attend to it (avoidance), or lash

Figure 1. Inserts in Canada

out at it in anger (reactance). To minimize such defensive responses to HWLs and maximize their desirable effects, empirical evidence^{28 29} and diverse behavior change theories^{27 30 37-41} highlight the importance of efficacy messages like those that are included on Canadian inserts. However, almost no research has assessed whether efficacy messages on labels can promote smoking cessation. Our proposed study will fill this critical gap.

2.2 BACKGROUND

Scientific Premise & Conceptual Model

Our central hypothesis is that inserts with efficacy messages promote smoking cessation-related outcomes. Other primary hypotheses (Table 1) follow from our conceptual model (Figure 2). Figure 2 shows our synthesis of theoryand empirically-based propositions on which our study is based. We posit that insert exposure will increase efficacy beliefs that, in turn, increase guit motivation and quit behaviors. Prominent pictorial HWLs will increase quit motivation and behaviors primarily by generating negative affect around smoking, although some smokers will have defensive responses (e.g., avoidance, reactance) to HWLs. HWLs and inserts will interact synergistically. HWL-generated negative

Table 1. Study 1 Hypotheses: EMA Randomized Controlled Trial

Main effects of condition on cessation-related outcomes & primary mediators

- **H1:** Exposure to packs with inserts will result in stronger efficacy beliefs (e.g., self-efficacy, response efficacy) than packs without inserts, which, in turn, will lead to stronger cessation-related outcomes (e.g., interpersonal discussions about quitting, foregoing cigarettes, reduced consumption, intention to quit).
- **H2:** Exposure to packs with large pictorial HWLs will produce stronger negative affective responses toward smoking than text-only HWLs, which, in turn, will lead to stronger cessation-related outcomes (see H1).

Interactions between inserts and HWLs & explanatory mechanisms

- H3: Insert effects on cessation-related outcomes (see H1) will be stronger when accompanied by pictorial HWLs than by text-only HWLs, because pictorial HWLs will promote greater attention to inserts ("spotlight" effect of negative affect).
- **H4:** Pictorial HWL effects (relative to text-only HWLs) on cessation-related outcomes (see H1) will be stronger when accompanied by inserts, because inserts will promote efficacy beliefs and thereby reduce defensive responding.

Interactions between condition & smoker characteristics

- **H5:** Pictorial HWL effects (relative to text-only HWLs) on key outcomes (see H1) will be moderated by baseline self-efficacy to quit, such that the association will be stronger amongst smokers whose baseline self-efficacy is higher than lower (H5a). Moderation effects will be weaker when packs include inserts (H5b).
- H6: Insert effects will be moderated by education, literacy, and delay discounting, such that the association with key outcomes (see H1) will be stronger for smokers with higher education, higher literacy, and lower delay discounting than for their counterparts (H6a). Moderation effects will be weaker when inserts are accompanied by pictorial HWLs due to because pictorial HWLs will have stronger effects among smokers with lower education and lower literacy (H6b).

affect will promote attention to and processing of insert messages ("spotlight" effect). Efficacy beliefs generated from inserts (or pre-existing efficacy beliefs) will reduce defensive responses to HWLs. Education will modify labeling effects given evidence of stronger responses to pictorial HWLs among smokers with lower education and literacy,⁴² although they face large barriers to cessation.^{43 44} Greater delayed discounting, or valuation of present rewards (e.g., nicotine administration) over future rewards (e.g., cessation benefits), is associated with failed cessation,^{45 46} and should reduce label effectiveness. Finally, labeling effects will vary over time, due to both message "wear out"⁴⁷⁻⁴⁹ and the dynamic nature of quit motivation.^{22 50 51}

Dual system model: We base our conceptual model in dual-system models of decision making, ⁵⁴ The "deliberative mode" is conscious, analytical, and slow, reflecting standard cognitive explanations of how people engage with information and make decisions.⁵⁵ By contrast, the "experiential mode" involves easier, more rapid and spontaneous feelings about information. The "affect heuristic," wherein decision making is based on "gut" feelings, is based in this mode.^{56 57} Repeated exposures to information shape the feelings that make information meaningful and likely to influence people's decisions.^{58 59} Deliberative and experiential modes are not mutually exclusive, and one may predominate over the other at any moment. In the context of repeated message exposures – as with cigarette labels – the relative prominence of either mode will vary over time because of situational and personal factors, including changes in motivation to process messages.

Studies support the central role of negative affect in explaining HWL effects on cessation-related intentions and behaviors. Compared to text-only warnings, prominent pictorial HWLs elicit more negative affect, including fear, sadness, and disgust,^{5 60} which are highly correlated in HWL studies that have considered them.^{26 61 62} These results support constructionist views of emotion that emphasize emotional valence and arousal⁶³ rather than differential effects of discrete emotions on intentions and behaviors.^{64 65} In explaining HWL effects on cessation-related outcomes, negative affect appears more important than cognitive risk perceptions.^{5 26 60}

Affective responses can function as: 1. information; 2. motivator; and 3. "spotlight".^{22 53} ^{58 59 66} As information, affective responses occur in the experiential mode, involving relatively rapid impressions of an object or information. As a motivator, positive affect prompts pleasant behaviors while negative affect inhibits behaviors that feel bad or could harm oneself. This "approach-avoidance" function to affect is central to implicit motivation models of HWL effects.^{67 68} As a spotlight, affect can lead to deliberative decision making by promoting greater scrutiny of information related to the source of the affective response.²² Prior HWL studies have found that affect functions as "information" (e.g., risk perception), "motivator" (interpersonal communication about HWLs;^{49 69 70} reduced smoking satisfaction;⁷¹ foregoing cigarettes;⁷²⁻⁷⁷ reduced cigarettes per day⁷⁸⁻⁸¹) and "spotlight" (e.g., frequency of thinking about risks^{72 76}), all of which can independently predict subsequent cessation behavior.⁴⁹ Our study will provide a novel test of the "spotlight" function of negative affect, which we expect to promote processing of efficacy messages on inserts. This conceptualization is consistent with the "emotional flow" of persuasion,^{82 83} wherein fear appeals (e.g., HWLs encountered on the pack exterior) are most effective when followed by efficacy messages (e.g., inserts encountered after opening a pack) that generate hope about being able to escape the danger.

Defensive responses to HWLs: Fear arousing messages can produce "defensive responses" (e.g., avoidance, reactance) that, according to some theories, lead to message rejection.^{28 31-33 35} ³⁶ Eye-tracking research is mixed regarding whether smokers avoid HWLs by directing their attention more to branded parts of the pack than HWLs.^{84 85} Other experiments have found that fear arousing HWLs result in greater reactance (i.e., anger from perceived manipulation),^{35 36 86} ⁸⁷ which can lead to message rejection.^{88 89} Recent RCTs find that reactance offsets the effectiveness of pictorial HWLs for a subgroup of smokers, but these effects do not appear to outweigh the effectiveness of HWLs for smokers overall.^{26 77} No studies have examined whether efficacy messages enhance the effectiveness of HWLs by dampening defensive responses, as suggested by theory. The strongest critics of pictorial HWLs highlight the need for this research.³¹⁻³⁴

Efficacy beliefs and messages: Behavior change theories, such as the Extended Parallel Processing Model (EPPM)^{28 41} and Protection Motivation Theory (PMT),³⁰ posit that fear appeals will be most effective when message recipients believe the benefits of protective action (i.e., response efficacy) and are confident they can engage in this action (i.e., self-efficacy). Indeed, self-efficacy to quit predicts cessation behavior,^{14 73 77 90-94} and increasing self-efficacy to quit promotes smoking cessation.⁹⁵⁻⁹⁸ Fear appeals generally produce desired effects independent of efficacy beliefs,^{28 29 73 77} although HWLs can have weaker effects for smokers with lower self-efficacy.⁹⁹⁻¹⁰¹ No research, however, has examined whether including strong efficacy messages alongside fear-arousing HWLs will enhance desired outcomes, particularly for smokers with lower self-efficacy.

HWL messages that countries have adopted and that have been used in experimental research minimally address efficacy beliefs by including information about cessation resources (e.g., quitlines, websites).¹⁰²⁻¹⁰⁷ However, most smokers quit without using these resources,¹⁰⁸⁻¹¹¹ whose inclusion on new HWLs in Australia did not change smokers' self-efficacy to quit.¹¹² To meaningfully change efficacy beliefs, labels likely require elaborated messages like those on Canadian inserts, which underscore cessation benefits and provide cessation tips that do

not require cessation resource use. Our preliminary studies support this approach, including our post-implementation observational studies in Canada that found independent effects of reading inserts on subsequent sustained smoking cessation (Figure 3).^{14 113} No research has examined the conditions under which smokers are most likely to process efficacy messages

and, thereby, increase their efficacy beliefs. Consistent with the "spotlight" function of affect⁵³ and theories of "emotional flow,"⁸² we hypothesize that efficacy messages on inserts will most influence cessation-related outcomes among smokers exposed to fear arousing pictorial HWLs on packs.

